8.2 RANDOMIZATION

At Day 1, all eligible subjects will be randomized [REDACTED] to one of the three treatment arms (NGM282 1 mg, NGM282 3 mg, or placebo) in a 1:1:1 ratio. The randomization will be stratified by UDCA status (yes/no), to ensure an even distribution across the three treatment groups. That status will be based on concomitant medication history. Additional randomization specifications will be detailed in the randomization plan.

8.3 TEST OF HYPOTHESIS AND SIGNIFICANCE LEVELS

The null hypothesis being tested for this study will be that there is no difference between the active (1 mg or 3 mg NGM282, as applicable) and the Placebo treatment groups at Week 12 in the population mean change from Baseline in ALP. However, trial success will depend on both rejection of that null hypothesis at the 5% two-sided significance level, and observing the difference between either of the NGM282 groups and the placebo group, in the LS mean changes from Baseline of at least 30% of the placebo LS mean change from Baseline.

8.4 ANALYSIS SETS

The analysis sets are detailed below. Details of any others will be described in the SAP.

8.4.1 Randomized Set

All randomized subjects will be included in the Randomized Set. In analyses using this set, subjects will be grouped according to randomized treatment if this differs from actual treatment received.

8.4.2 Safety Set

All randomized subjects who receive at least one dose (full or partial) of study drug and have at least one post-dose safety evaluation will be included in the Safety Set. In analyses using this set, subjects will be grouped according to actual treatment received if this differs from the randomized treatment.

8.4.3 Full Analysis Set

All randomized subjects who receive at least one dose (full or partial) of study drug and have at least one valid, non-missing post-dose efficacy/PD parameter value will be included in the Full Analysis Set (FAS). This will be the set for the primary analyses of efficacy and PD endpoints. In FAS analyses, subjects will be grouped according to randomized treatment if this differs from actual treatment received.

8.4.4 Per Protocol Set

The Per Protocol Set (PPS) will constitute a subset of the FAS. It will include subjects who have at least one valid, non-missing post-dose ALP measurement. In addition, FAS subjects who deviate from the conduct of the study or have an AE deemed by the Medical Monitor to be impactful on the primary endpoint will be excluded from the PPS. In associated analyses, subjects will be grouped according to actual treatment received, if it differs from the randomized treatment.

8.4.5 Pharmacokinetic Set

All randomized participants who receive at least one dose (full or partial) of blinded drug, had a pre-dose (Baseline) blood draw, and provided at least one qualified (above the limit of quantification) post-dose sample will be included in the PK Set. Subjects with protocol violations will be assessed by the medical monitor for inclusion in this set. In associated analyses, subjects will be grouped according to the actual treatment received, if it differs from that to which the subject was randomized.

8.5 SUBJECT DISPOSITION

Individual data listings for subject disposition will be presented for each subject, including enrollment date, treatment start date, treatment discontinuation date, discontinuation reason, and analysis set flags. The number and percentage of subjects entering and discontinuing the study will be presented by treatment group. The reasons for discontinuation will also be summarized. Subject disposition will be summarized using the FAS.

8.6 TREATMENT EXPOSURE

Measures of extent of treatment exposure include the total number of doses per subject and compliance. Treatment compliance is defined as the number of doses administered per protocol/number of doses prescribed per protocol. These measures will be summarized using the Safety Set.

8.7 PROTOCOL DEVIATIONS

Protocol deviations will be summarized using the FAS.

8.8 DEMOGRAPHICS AND OTHER BASELINE CHARACTERISTICS

Demographics, medical history, and other Baseline characteristics will be summarized using the Randomized Set, FAS, and Safety Set.

8.9 EFFICACY AND PHARMACODYNAMICS

8.9.1 Efficacy and Pharmacodynamic Endpoints

The primary efficacy endpoint is the mean change in ALP from Baseline at Week 12.

The secondary efficacy and PD endpoints are the following:

- Percent change from Baseline at Week 12 in ALP
- Absolute and percent changes from Baseline at Week 12 in the following:
 - ALT, AST, bilirubin (total, direct), and GGT
 - C4 and serum bile acids
 - Total cholesterol, HDL cholesterol, LDL cholesterol, and triglycerides
- Bile-mediated absorption as measured by fat-soluble vitamins and fecal fat content
- Changes in pruritus and fatigue, as measured by the weekly mean of the daily pruritus and fatigue NRS assessments
- Incidence and severity of IBD-associated intestinal symptoms
- Incidence and severity of acute cholangitis

Exploratory PD Endpoints:

- [REDACTED]
- [REDACTED]
- [REDACTED]

8.9.2 Analysis of Primary Efficacy Endpoint

As the primary efficacy analysis, the population mean change in ALP from Baseline to Week 12 will be compared between treatment groups using a mixed-effect model repeated measures (MMRM) analysis of covariance (ANCOVA) of the primary efficacy endpoint, using the FAS. The model will contain treatment group, visit, treatment group by visit interaction, UDCA (yes/no), treatment group by UDCA interaction, and diabetic status as classification variables and the Baseline value as a continuous covariate. An unstructured covariance matrix will be assumed; however, if the modeling using that matrix does not converge, then other matrices will be explored. For each treatment and treatment comparison versus placebo, the least squares mean, associated standard error (SE), 95% confidence interval, and corresponding p-value will be presented. The overall type 1 error rate for the two primary comparisons versus placebo will be controlled using the step-down Dunnett multiple-testing procedure ([Dmitrienko and D'Agostino 2013](#)).

As secondary analyses within the same MMRM, the linear combinations

$$\mu_1 - \mu_3$$

and

$$(\mu_1 + \mu_3)/2 - \mu_p$$

will be estimated, where μ_1 , μ_3 , and μ_p are the population LS means for the primary efficacy endpoint of the 1 mg NGM282, 3 mg NGM282, and placebo groups, respectively.

Further explanatory variables may be included in additional modeling using the FAS, similar to the primary efficacy analysis, depending on the relevance to the endpoint; such modeling will be specified in the SAP.

If strong evidence of marked deviations from normality is noted in the distribution of the residuals of the primary MMRM ANCOVA, then FAS analyses using data transformations of the primary efficacy endpoint, and/or non-parametric approaches, will be explored.

As sensitivity analyses,

- a. The primary analysis for the primary endpoint will be repeated for the PPS.
- b. The treatments will be compared with respect to the population mean of the primary endpoint using the FAS and an ANCOVA model having treatment group, UDCA (yes/no), and treatment by UDCA interaction as classification variables, and the baseline value as the continuous covariate. The overall type 1 error rate for the two pairwise comparisons versus placebo will be controlled using the step-down Dunnett multiple-testing procedure. Missing data will be imputed using the last post-baseline observation carried forward methodology. Subjects with no post-baseline observations will be excluded.

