7.1.1. Primary Analysis

The primary analysis will be performed on the FAS to evaluate the treatment effect of NGM282. The mean change in ALP from Baseline at Week 12 will be compared between each of the two treatment groups (NGM282 1 mg or 3 mg, as applicable) and the placebo group.

Mixed-effect model repeated measures (MMRM) analysis of covariance (ANCOVA) of mean change in ALP from Baseline at Week 12 will be used to compare the difference between treatment groups. Mathematically stated:

H_0 : Mean change in ALP from Baseline at Week 12_{NGM282 1 mg} = Mean change in ALP from Baseline at Week 12_{placebo},

and

Mean change in ALP from Baseline at Week 12_{NGM282 3 mg} = Mean change in ALP from Baseline at Week 12_{placebo}

H_1 : Mean change in ALP from Baseline at Week 12_{NGM282 1 mg} \neq Mean change in ALP from Baseline at Week 12_{placebo},

[figure not shown]
or

Mean change in ALP from Baseline at Week 12_{NGM282 3 mg} \neq Mean change in ALP from Baseline at Week 12_{placebo}

Mean change in ALP from Baseline at Week 12 will be evaluated using the MMRM analysis adjusting for treatment group, visit, treatment group by visit interaction, UDCA use, treatment group by UDCA use interaction as classification variables and the Baseline value as covariate. For each treatment and treatment comparison versus placebo, the least squares mean, associate standard error (SE), 95% confidence interval and corresponding p-value will be present. The overall type I error rate for the two primary comparisons versus placebo will be controlled using the step-down Dunnett multiple-testing procedure [Dmitrienko and D'Agostino (2013)].

With the same model, linear combinations $\mu_1 - \mu_3$ and $(\mu_1 + \mu_3)/2 - \mu_p$ will be estimated, where μ_1 , μ_3 , and μ_p are the population LS means for the primary efficacy endpoint of the 1 mg NGM282, 3 mg NGM282, and placebo groups, respectively.

The relevance of the explanatory variables to the mean change in ALP from Baseline at Week 12 will be checked. All relevant explanatory variables will be included in the primary analysis model with FAS.

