8.7. Local Injection-Site Symptom Assessments

The injection-site evaluation will be made using LISSA at Day 1, Weeks 1, 2, 4, 8, 12 and 16 (End of study). LISSA scores will be documented on the subject's eCRF.

A summary to the evaluated ISR will be presented with number and percentage of subjects at each time point by treatment group using Safety Set.

10. Data Monitoring Committee

A Data Monitoring Committee (DMC) will be established in order to protect subject welfare, preserve study integrity, and provide recommendations as needed regarding study conduct. The DMC will be comprised of two external liver disease clinical experts as well as a statistician and a medical team member from the sponsor. The DMC will meet at predefined time points and on an as-needed basis based on enrollment, treatment milestones, and safety. Formal minutes and recommendations will be provided by the DMC to the sponsor regarding additional data requests and the continuation of the conduct of the study as outlined in the current protocol. The DMC will operate under the guidance of an agreed-upon charter.

The analyses and outputs provided to the DMC are a subset of the IA and Full Study SAP.

11. Changes in the Planned Analysis

The descriptive summarization and MMRM ANCOVA model analyses for Change from Baseline in (5-D Pruritus Scale and Pruritus and Fatigue) were removed from the current SAP. At this time only the listings to display the data are planned.

The analyses for acute cholangitis were removed from the current SAP. At this time only the listings to display the data are planned.

The C4 and Serum bile acids, Fecal microbiome composition and PK data will not be transferred to [REDACTED] the Contract Research Organization performing the analyses of this SAP. Therefore, the analyses of these data were removed from this SAP.

12. References

Chuck Kincaid (2005). Guidelines for Selecting the Covariance Structure in Mixed Model Analysis, Proceeding of the 30th SAS Users Group International Conference.

Hollander, Myles, Douglas A. Wolfe. (1973),*Nonparametric Statistical Methods*, New York: John Wiley & Sons, 75-82.

Liu, H. (2007) Cochran-Armitage Trend Test Using SAS, *PharmaSUG 2007*, SP05.

13. Appendices

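### The primary MMRM is not fixed across the documents: the protocol includes diabetic status, the interim SAP omits it without recording the change, and the SAP lets other covariates in through an undefined check

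*Protocol*

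**What the plan says.** Protocol 8.9.2 defines the primary efficacy analysis as an MMRM on the Full Analysis Set. The terms are treatment group, visit, their interaction and UDCA, followed by "treatment group by UDCA interaction, and diabetic status as classification variables and the Baseline value as a continuous covariate".

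SAP 7.1.1 gives the same list up to the visit interaction and continues with "UDCA use, treatment group by UDCA use interaction as classification variables and the Baseline value as covariate". Diabetic status is absent. The SAP then adds a rule of its own: relevance of explanatory variables to the endpoint will be checked, and "All relevant explanatory variables will be included in the primary analysis model with FAS". No test, threshold or candidate list is given. On the same subject the protocol says only that "Further explanatory variables may be included in additional modeling using the FAS, similar to the primary efficacy analysis", with that modeling to be specified in the SAP.

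SAP Section 11 is where departures are declared. One entry begins "The descriptive summarization and MMRM ANCOVA model analyses for Change from Baseline" and concerns pruritus and fatigue. Another reads "The analyses for acute cholangitis were removed from the current SAP". The last covers C4, bile acids, fecal microbiome and PK. None concerns the primary model.

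The Introduction of the SAP says that it covers the interim analysis under protocol Amendment 2. SAP Section 10 refers to a full-study SAP, which is not among the documents.

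**The concern.** A confirmatory comparison needs one model, chosen before anyone sees data by arm. Here the protocol names one model and the interim SAP another. The SAP's relevance check could then bring diabetic status, or any other covariate, into the primary model on the strength of the data.

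Timing adds to this. Protocol 8.10.9 plans an unblinded interim once about 24 subjects have completed Week 12, with efficacy among the matters assessed. The opening of Protocol Section 8 requires the detailed SAP only before database lock. Nothing in the text prevents the final model from being settled after interim results exist. With 16 expected completers per arm, a borderline p-value can fall on either side of the threshold depending on the model.

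**Working it through.** **1. The passages side by side.**

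| Place | Treatment, UDCA, interaction, baseline | Diabetic status | Other covariates |
|---|---|---|---|
| Protocol 8.9.2, primary MMRM | yes | yes | additional modeling only |
| SAP 7.1.1, primary MMRM | yes | no | any found relevant, in the primary model |
| Protocol 8.1 item D, power model | yes | no | none |
| Protocol 8.9.2, sensitivity analysis b | yes | no | none |

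Sensitivity analysis b is "an ANCOVA model having treatment group, UDCA (yes/no), and treatment by UDCA interaction as classification variables", plus baseline. Diabetic status is not a stratification factor (Protocol 8.2) or a listed baseline disease characteristic (SAP 5.2), and neither document defines it.

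**2. The plan's own power.** Inputs from Protocol 8.1: changes of -75 and -475 against 0 in equal cells, SD 200, 16 completers per arm, two-sided level 0.027.

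- Mean difference = (75 + 475)/2 = 275.
- SE of the difference = 200 x sqrt(2/16) = 70.7, so the standardized difference is 275/70.7 = 3.89.
- Power is 95.3% by the normal approximation and 94.1% with a t reference on 41 df. The plan's figure of at least 90% is reproduced.
- The simulated single-step Dunnett level is 0.0273, matching 0.027.

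**3. Can the choice of model change the verdict?** Week 12 ANCOVA stood in for the MMRM, with 16 per arm and UDCA split 8/8. One dose was compared with placebo at the single-step Dunnett critical value of 2.29, with the 30% condition applied, in 3,000 runs per scenario. The numbers of diabetics, their effect, the differences other than -275 and the nonzero placebo changes are assumptions.

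| Diabetics of 48 | True difference | Diabetic effect | Placebo change | Significant, SAP model | Significant, protocol model | Verdict differs |
|---|---|---|---|---|---|---|
| 3 | -275 | 0 | 0 | 93.6% | 92.8% | 1.7% |
| 3 | -150 | 0 | 0 | 41.9% | 41.0% | 4.1% |
| 1 | -150 | 0 | 0 | 42.1% | 41.1% | 4.5% |
| 3 | -150 | 200 | 0 | 41.2% | 42.1% | 7.6% |
| 1 | -150 | 200 | 0 | 41.4% | 41.3% | 5.6% |
| 3 | -75 | 200 | 0 | 12.0% | 12.2% | 4.3% |
| 3 | -150 | 0 | -100 | 43.6% | 42.5% | 4.2% |
| 1 | -150 | 200 | +100 | 42.1% | 41.7% | 7.0% |

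Neither model is systematically more powerful; they disagree in individual data sets. In the fourth row, reporting whichever model succeeds would give (41.2 + 42.1 + 7.6)/2 = 45.5% successes, 3 to 4 points above either model alone. The null case was not simulated, so type I error inflation is not quantified.

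**4. The 30% condition in Protocol 8.3.** A significant result failed it in 0 of 3,000 runs under the SAP model in every scenario. Under the protocol model the worst case was 1 of 3,000 (0.03%), in the last row.

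**5. LS means if diabetic status is kept.** With equal weights on its two levels, each arm's LS mean is evaluated at a half-diabetic population. Ignoring UDCA and baseline, with k diabetics of 48 spread evenly over the arms:

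Var(placebo LS mean) = 200²/16 + (0.5 - k/48)² x 200² x (1/k + 1/(48 - k)).

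- k = 3: 2500 + 0.4375² x 40000 x (1/3 + 1/45) = 2500 + 2722 = 5222, so SE = 72.
- Without the term: sqrt(2500) = 50.

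The full design matrix, with UDCA, its interaction and baseline and with diabetics allocated at random, gives a median SE of 118 for 1 diabetic, 85 for 2, 74 for 3, 64 for 5, 58 for 8, 53 for 12 and 51 for 24, against 50.2 without the term. With observed-margin weights it is 50.5 to 50.8 throughout. The treatment-difference SE is 71.1 without the term and 71.8 to 72.2 with it. Under equal weights and k = 3, the arm estimate also shifts by 0.4375 times the diabetic effect, about 44 units per 100.

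**The case against.** **The SAP is the interim one.** Two competing models for the final analysis have not been shown, because the full-study SAP is unseen. This stands and limits the scope. It does not remove the point: the interim efficacy assessment already departs from the protocol's model without saying so.

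**The documents may be different versions.** The SAP is written to Amendment 2. Its schedule (Appendix 13.1) has a TSH row that Protocol Table 5.5-1 lacks. Its colonoscopy footnote is not limited to IBD patients, and its rating-scale diary footnote omits Day 1. Diabetic status may have entered or left with an amendment, so a silent change by the SAP authors is unproven. This also stands, but the texts still need to agree.

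**A covariate need not be a stratification factor or appear in the power model.** True. Diabetes recorded as medical history would also be tabulated under SAP 5.3. These absences suggest that the protocol term is the odd one out; they do not prove it an error.

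**A stronger reading.** A reader might infer that the protocol's model makes the placebo LS mean unstable and so puts the success rule at risk. The documents do not support this. The inflation needs both equal-weight LS means and few diabetics, and neither is stated. It disappears with observed margins or a near-even split. The additive term cancels from the treatment contrast. Because Protocol 8.1 assumes a placebo change of 0, 30% of that change is near zero under either model.

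**Conclusion.** The primary model is not fixed across the protocol and the interim SAP. They differ on diabetic status, Section 11 is silent, and the SAP's relevance check leaves the primary model dependent on the data, contrary to the protocol. The choice matters in borderline cases: the verdict on one dose differed in 1.7% to 7.6% of simulated runs, almost entirely through the p-value. Those figures rest on SD 200, 16 completers per arm, an assumed 1 or 3 diabetics, and a Week 12 ANCOVA in place of the full MMRM with step-down testing.

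The precision of the treatment difference is essentially the same under either model, and the effect on the 30% condition is negligible. LS-mean inflation is a conditional reporting issue, to be dealt with only if the term is kept. Given the interim scope of the SAP and the possible version difference, this is a should-fix reconciliation, not a threat to the trial's validity.

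**What to change.** 1. Name one primary model, in identical terms, in the protocol, the interim SAP and the full-study SAP, before any unblinding. The simplest choice is to drop diabetic status from Protocol 8.9.2, which then matches the power model and sensitivity analysis b, and to show a model with diabetic status as a sensitivity analysis.
2. Record the change and its reason in SAP Section 11, and state which protocol version each SAP follows.
3. Delete the relevance check from the primary analysis in SAP 7.1.1. Put any further covariates into pre-named additional models, as the protocol provides.
4. If diabetic status is kept instead, define it (source and time point), add it to both SAPs, and specify LS means at observed margins.

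The cost is wording, with no new data and no change to sample size. Dropping the term also needs a protocol change, with the sponsor and investigator agreement and ethics committee notification in Protocol 10.1 and 10.4. Keeping the term would change the SAPs and add a definition.

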5.3 DISCONTINUATION OF STUDY TREATMENT IN AN INDIVIDUAL SUBJECT

Study treatment will be discontinued if any of the following CTCAE categories or abnormal elevations in liver function tests occurs on-treatment:

- Any Grade 3 TEAE related to study drug
- Any Grade 4 or higher TEAE
- Elevation of ALT **and** total bilirubin > 2 times above subject-specific baseline value calculated using the median of the Screening and Day 1 value
 - ALT, AST, and total bilirubin must be re-tested within 72 hours.
 - Subjects with persistent elevations should be discontinued from treatment, independent of whether or not they are symptomatic.
- Elevation of ALT > 2 times above subject-specific baseline
 - ALT, AST, and total bilirubin must be re-tested within 72 hours.
 - Subjects with persistent elevations who are asymptomatic may continue treatment under protocol-defined *close observation* criteria.
 - Subjects with persistent elevations who are symptomatic must discontinue treatment.
 - Subjects continuing treatment under *close observation* should implement study procedures and assessments as part of the study conduct:
 1. Repeat liver enzyme and serum bilirubin tests two or three times weekly. The frequency of retesting can decrease to once a week or less if abnormalities stabilize or the trial drug has been discontinued and the subject is asymptomatic.
 2. Repeat additional tests to evaluate liver synthetic function (e.g., INR, direct bilirubin) as appropriate.
 3. Obtain a detailed history of symptoms and prior or concurrent diseases.
 4. Obtain a history of concomitant drug use (including nonprescription medications and herbal and dietary supplement preparations), alcohol use, recreational drug use, environmental toxin exposure, and special diets.
 5. Rule out acute viral hepatitis and other acute or chronic hepatobiliary diseases.

Dose reductions or increases are not allowed as part the study conduct.

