8.1 SAMPLE SIZE

A sample size of 20 subjects randomized per treatment group was chosen in light of logistical needs and so as to accumulate sufficient safety data on NGM282. The associated power to detect a treatment difference in the primary efficacy analysis, for either NGM282 comparison versus placebo, is at least 90%, based on the following assumptions:

A. ALP Population Mean Change from Baseline:

		NGM282 (either 1 mg or 3 mg)		Placebo
Subjects taking UDCA at Baseline		–75	0	
Subjects not taking UDCA at Baseline		–475	0	

UDCA = ursodeoxycholic acid.

B. Equal numbers of completing subjects for each of the four cells above
C. Population (not sample) standard deviation (SD) between subjects within each of the four cells above: 200
D. Analysis of variance with treatment, UDCA (yes/no), treatment with UDCA (all as classification variables), and baseline value (as a continuous covariate) in the model
E. 20% dropout rate, from randomization to Week 12, yielding 16 completing subjects per treatment group
F. Dunnett's 1-step adjustment for multiplicity, requiring a type 1 error rate of 0.027 (2-sided) for each comparison versus placebo

Assumptions underlying the means and SDs are based on studies evaluating UDCA as a first-line therapy and in studies where secondary or combination therapies with UDCA have been utilized. The power in the primary efficacy analysis may be slightly higher, since it incorporates Dunnett's step-down adjustment and utilizes repeated measures to reduce the power losses due to dropouts. On the other hand, power may decrease slightly, to the degree that unequal numbers of subjects are randomized taking and not taking UDCA. In addition, the probability that the observed least square (LS) mean treatment difference exceeds 30% of the placebo LS mean change has not been examined.

To randomize 60 subjects, approximately 90 will be screened.

If, in contrast, the population SD is 300, the power is roughly 81% for each NGM282 comparison versus placebo.

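### LOCF is the only missing-data sensitivity analysis for Week 12 ALP in the supplied documents; its bias has no known sign, so it does not bound the effect of dropout that is not at random

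*Protocol*

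**What the plan says.** Protocol section 8.9.2 compares the mean change in ALP to Week 12, "compared between treatment groups using a mixed-effect model repeated measures (MMRM) analysis of covariance (ANCOVA) of the primary efficacy endpoint, using the FAS". No imputation is described, so the result rests on the data being missing at random.

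Two sensitivity analyses follow.

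- Analysis (a): "The primary analysis for the primary endpoint will be repeated for the PPS".
- Analysis (b) is an ANCOVA on the FAS with treatment, UDCA, their interaction and baseline, again with step-down Dunnett. Its missing-data rule is "Missing data will be imputed using the last post-baseline observation carried forward methodology", and "Subjects with no post-baseline observations will be excluded".

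Section 8.1 plans for a "20% dropout rate, from randomization to Week 12, yielding 16 completing subjects per treatment group".

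No estimand is stated. Section 5.4 asks for efforts to obtain the Week 12 and Week 16 assessments after premature discontinuation, and section 5.6.7 schedules a 4-week follow-up visit for early withdrawals. The documents do not say whether ALP measured after stopping drug enters the MMRM or the LOCF analysis.

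The SAP supplied describes itself, in its introduction, as the interim plan. Its section 7.1.1 has the MMRM and neither sensitivity analysis, and its section 11 does not record their removal. Section 10 refers to a full-study SAP, which was not supplied.

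**The concern.** A missing-data sensitivity analysis should show how far the conclusion depends on the missing-at-random assumption, above all in the direction that hurts the drug. Analysis (a) changes the population and keeps the same assumption. Analysis (b) replaces that assumption with another one, that ALP stays at its last recorded value.

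Where that value was taken on drug, LOCF credits the reduction after treatment has ended. MMRM does much the same by giving the subject the trajectory of similar subjects in the same arm. Both can then lean the same way, and a reader who sees them agree may take that as evidence of robustness.

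Dropout related to treatment is plausible here, though not established. Section 5.3 stops treatment for, among other events, "Any Grade 3 TEAE related to study drug". Section 2.4 reports diarrhoea in 21.4% and 25.0% of the active arms of the PBC trial, against 6.7% on placebo.

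A second weakness is that analysis (b) also drops diabetic status and the repeated-measures structure. If it differs from the MMRM, the difference cannot be put down to missing data alone.

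**Working it through.** **Inputs from protocol section 8.1.** The mean change on NGM282 is -75 with UDCA and -475 without, and 0 on placebo in both strata. Cells are equal in size, the SD is 200, and 16 of 20 subjects per arm complete. The test is described as "requiring a type 1 error rate of 0.027 (2-sided) for each comparison versus placebo". ALP figures below are in the units of that section, which it does not name.

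Planned mean effect: D = (-75 - 475)/2 = -275.

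**The plan's own power figure.** SE = 200 × √(2/16) = 70.7, so 275/70.7 = 3.89. The critical value at two-sided 0.027 is 2.21, and Φ(3.89 - 2.21) gives about 95.3%. The noncentral t with 41 degrees of freedom (48 completers less 6 cell means and 1 covariate) gives 94.1%. Both meet the stated minimum of 90%.

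**Assumptions the documents do not supply.**

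- d is the dropout proportion, equal across the UDCA strata.
- f is the share of the Week 12 effect present at the carried value.
- g is the share of the effect still present at Week 12 after stopping.
- Placebo change is 0 throughout.
- Before they leave, dropouts resemble completers at the same visits.
- No off-drug ALP enters either analysis.

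**Expected differences from placebo.**

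- All randomised subjects, regardless of stopping: D × [(1 - d) + d × g]
- MMRM under missing at random: D
- LOCF: D × [(1 - d) + d × f]

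Subtracting, MMRM overstates the benefit by 275 × d × (1 - g), and LOCF by 275 × d × (f - g). The sign of the LOCF error is therefore the sign of f - g.

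**Results at the planned d = 0.20** (275 × 0.20 = 55). Positive entries overstate the benefit; negative entries understate it.

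| Retained off drug (g) | All-randomised effect | MMRM | LOCF, f = 0.25 | f = 0.5 | f = 0.75 | f = 1 | f = 1.25 |
|---|---|---|---|---|---|---|---|
| 0 | -220 | 55 | 13.75 | 27.5 | 41.25 | 55 | 68.75 |
| 0.5 | -247.5 | 27.5 | -13.75 | 0 | 13.75 | 27.5 | 41.25 |
| 1 | -275 | 0 | -41.25 | -27.5 | -13.75 | 0 | 13.75 |

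If ALP fell linearly to Week 12 and the effect were lost off drug, a last value at Week 4 gives f = 4/12 and an overstatement of 55 × 4/12 = 18.3. A last value at Week 8 gives f = 8/12 and 36.7. An f above 1 means that the effect wanes on treatment.

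With g = 0, the MMRM overstatement is 27.5 at 10% dropout and 82.5 at 30%.

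**What that means for power.** If the true difference is -220 and the standard error stays at 70.7, then 220/70.7 = 3.11 and Φ(3.11 - 2.21) is about 82%. The t version gives about 79%. Against 94% to 95% as planned, that is a loss of about 14 to 15 percentage points.

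**Could a carried value be off-drug?** A last dose by Day 59 puts the 4-week follow-up at or before Day 59 + 28 = Day 87, the upper limit of the Week 12 window in SAP section 3. The LOCF rule asks for the last post-baseline value, not the last on-treatment value, so an off-drug ALP could be the one carried, or could be the Week 12 value itself.

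**The case against.** The strongest reply is that LOCF need not share the MMRM's error. That would require the carried value to be on-drug and already near its Week 12 level, and the effect to be lost after stopping. The documents establish none of these. Section 2.4 reports a progressive fall in ALP to Day 28 in the PBC trial. Section 8.9.3 plans to compare slopes in Weeks 1–4 and Weeks 5–12, so the protocol does not presume a plateau. Visits after withdrawal are planned. This stands. A reader might infer that both analyses are biased towards NGM282 by 55, but that is one corner of the table, and elsewhere the LOCF error is smaller, zero or reversed.

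A reader might also infer from section 5.3 that missing data in the active arms will be drug-related. That does not follow. Section 5.3 governs stopping treatment, while leaving the study is covered in section 5.4. No discontinuation rates are given, section 2.4 calls most events in the PBC trial mild or moderate, and the 20% applies to every arm including placebo.

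The word bias presupposes a target. Under a hypothetical estimand, the effect had subjects stayed on drug, MMRM could be unbiased. The documents name no target, so this objection stands too, and it is a reason to state one.

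Finally, the full-study SAP might contain more. That cannot be checked here, so the point is confined to the supplied documents.

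These replies limit the size of the error. They do not make LOCF a test of missing at random: an analysis whose error can take either sign bounds nothing.

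**Conclusion.** The point holds in a limited form. In the supplied documents, LOCF ANCOVA is the only sensitivity analysis that changes the handling of missing Week 12 ALP, and nothing tests an unfavourable departure from missing at random.

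At 20% dropout with full loss of effect off drug, MMRM overstates the all-randomised effect of -220 by 55, and LOCF by about 14 to 55 for f from 0.25 to 1. With partial retention, LOCF may be unbiased or may understate. These figures rest on assumed values of f and g and on an all-randomised target. They give a range and do not forecast this trial's bias.

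The decision rule in section 8.3 includes "rejection of that null hypothesis at the 5% two-sided significance level", so it matters whether that result survives a less favourable assumption. No listed analysis would show this.

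This is a cheap improvement. It does not invalidate the primary analysis.

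**What to change.** Amend sensitivity analysis (b) in protocol section 8.9.2, and carry the same text into the full-study SAP:

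1. State the target estimand, and say whether ALP measured after stopping drug is used in the MMRM and in the sensitivity analyses.
2. Where ALP was observed in the Week 12 window after discontinuation, use it. Impute only Week 12 values that are actually missing.
3. Replace LOCF with placebo-based multiple imputation, analysed with the ANCOVA already specified. State how the imputations are pooled before step-down Dunnett is applied, for example by Rubin's rules for each comparison.
4. Add a delta-adjusted tipping-point run that makes the imputed values in the active arms progressively less favourable, and report the shift at which the adjusted conclusion changes.
5. Use the same baseline covariates as the primary model, including diabetic status, so that fewer things differ from the MMRM besides the missing-data assumption.
6. Keep LOCF, if at all, as a descriptive extra.

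The cost is SAP text and standard programming, with no extra data collection. The downside is a sensitivity estimate that will usually be less favourable to NGM282. With about four dropouts per arm planned (20 - 16), it will also depend on few subjects. The primary analysis is unchanged.
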